7.5.4 Physical examination

A listing of physical examination will be provided. The result of physical examination will be presented as “Not Done”, “Normal” or “Abnormal”.

7.5.5 B-ultrasound

B-ultrasound examination results will be recorded in 3-level (normal, abnormal not clinically significant, or abnormal clinically significant). All B-ultrasound data will be presented in the listing.

8. APPENDIX

8.1 Appendix 1: Description of Inclusion/Exclusion Criteria

Seq No	Type	Description
1	Inclusion	Age 18-60 years(inclusive)
2	Inclusion	Presence of HBsAg in serum at screening and for at least 6 months before screening assessment
3	Inclusion	Serum HBV DNA ≥ 2000 IU/mL if HBeAg positive at screening (with or without ALT elevation); or serum HBV DNA ≥ 200 IU/mL if HBeAg negative at screening (with or without ALT elevation)
4	Inclusion	
Pathologically or clinically diagnosed as advanced fibrosis or compensated cirrhosis defined as one of following(a or b) :
 
a. Liver biopsy showing advanced fibrosis or cirrhosis (Ishak score ≥ 4 or Fibrosis stage $\geq S3$ by Scheuer Score, or within the previous 6 months before baseline and provided that no treatment likely to improve liver histology has been taken since). The slides must be available for review by an independent histopathologist.
 
b. Clinical diagnosis: liver stiffness measure (LSM) > 12.4 kpa (ALT $> ULN$) or LSM > 9.0 kpa (ALT $\leq ULN$), plus one of the following:
 
 • Endoscopy-proven gastroesophageal or gastric varices, non-cirrhotic portal hypertension excluded; • Abdominal ultrasound or CT found changes indicating cirrhosis, irregular liver surface or nodularity, with/without splenomegaly(depth of spleen > 4.0 cm or spleen length > 13 cm); • Blood platelets $< 100 \times 10^9/L$ (and other causes of thrombocytopenia excluded);
5	Inclusion	
Ability to give written informed consent
 
A female is eligible to enter and participate in this study if she is of:
 
a. Non-childbearing potential (i.e., physiologically incapable of becoming pregnant, including any female who is post-menopausal), or
 
b. Child-bearing potential, has a negative urine pregnancy test at screening, and agrees to one of the following methods for avoidance of pregnancy during the period of the study and until 30 days after last dose of study medication:

6	Inclusion	
 • Oral contraceptive, either combined or progestogen alone. • Injectable progestogen. • Implants of levonorgestrel. • Oestrogenic vaginal ring. • Percutaneous contraceptive patches. • Intrauterine device (IUD) or intrauterine system (IUS) showing that the

Seq No	Type	Description
		
expected failure rate is less than 1% per year as stated in the IUD or IUS product label.
 
 • Has a male partner who is sterilised. • Double barrier method: condom and an occlusive cap (diaphragm or cervical/vault caps) with a vaginal spermicidal agent (foam/gel/film /cream/suppository).
7	Inclusion	Agreement not to participate in any other investigational trials or to undertake other HBV systemic antiviral or IFN regimens during participation in this study.
1	Exclusion	
Hepatocellular carcinoma as evidenced by one of the following:
 
 • Suspicious foci on ultrasound or radiological examination. • Normal ultrasound but serum alpha-fetoprotein >50 ng/ml at screening.
2	Exclusion	ALT >10 times ULN at screening or history of acute exacerbation leading to transient decompensation.
3	Exclusion	Documented co-infection with hepatitis A (HAV), hepatitis C (HCV), hepatitis delta virus (HDV), hepatitis E virus (HEV) or HIV. For HCV co-infection, subjects who are anti-HCV positive and in whom HCV RNA is undetectable are considered to be not eligible for enrolment.
4	Exclusion	Evidence of active liver disease due to autoimmune hepatitis (antinuclear antibody titre >1:160)
5	Exclusion	
Decompensated liver disease as indicated by any of the following:
 
 serum bilirubin >1.5 x ULN. prothrombin time activity <60% or INR >1.5 Serum albumin <32g/L. History of previous clinical hepatic decompensation (e.g., ascites, variceal bleeding, or encephalopathy).
6	Exclusion	Planned for liver transplantation or previous liver transplantation.
7	Exclusion	Creatinine clearance less than 70 ml/min.
8	Exclusion	Haemoglobin < 10 g/dL, white blood cell (WBC) count <1.5 x 10 ⁹ /L, platelets < 50 x 10 ⁹ /L.
9	Exclusion	Any serious or active medical or psychiatric illnesses other than hepatitis B which, in the opinion of the Investigator, would interfere with subject treatment, assessment or compliance with the protocol. This would include any uncontrolled clinically significant renal, cardiac, pulmonary, vascular, neurogenic, digestive, metabolic (diabetes, thyroid disorders, adrenal disease), immunodeficiency disorders, pathological fractures or cancer.
10	Exclusion	Active alcohol or drug abuse or history of alcohol or drug abuse considered by the Investigator to be sufficient to hinder compliance with treatment, participation in the study or clinical significance of results.
11	Exclusion	A female who is breastfeeding or plan to breastfeed.

Seq No	Type	Description
12	Exclusion	Use of immunosuppressive therapy, immunomodulatory therapy (including IFN or thymosin α_2), systemic cytotoxic agents, chronic antiviral agents including Chinese herbal medicines known to have activity against HBV (e.g., LAM, adefovir, ETV LdT or hepatitis B immunoglobulin (HBIg)) within the previous 6 months prior to screening into this study
13	Exclusion	Have ever received TDF or any medicinal products containing the above mentioned antiviral agents or any investigative anti-HBV treatments (e.g., emtricitabine (FTC), (2R, 4R)-4-(2,6-Diaminopurin-9-yl)-1,3-dioxolan-2-yl]methanol (DAPD) and 1-(2-fluoro-5-methyl-beta, Larabinofuranosyl) uracil (L-FMAU)).
14	Exclusion	History of hypersensitivity to nucleoside and/or nucleotide analogues and/or any component of study medication.
15	Exclusion	Therapy with nephrotoxic drugs (e.g., aminoglycosides, amphotericin B, vancomycin, cidofovir, foscarnet, cis-platinum, pentamidine etc.) or competitors of renal excretion (e.g., probenecid) within 2 months prior to study screening or the expectation that subject will receive any of these during the course of the study.
16	Exclusion	Inability to comply with study requirements as determined by the study Investigator.

8.2 Appendix 2: CHILDS-PUGH SCORE*

Component	Score Given

 CCI - This section contained Clinical Outcome Assessment data collection questionnaires or indices, which are protected by third party copyright laws and therefore have been excluded. 
	CCI

Childs-Pugh Classification

Childs-Pugh Class CCI = score CCI

Childs-Pugh Class CCI = score CCI

Childs-Pugh Class CCI = score CCI

* Reference: Haozhu Chen, Guowei Lin. Practice of internal medicine. Edition 13. Beijing: People's Medical Publishing House, 2009:2082

8.3 Appendix 3: Treatment-emergent Laboratory Abnormalities

Grading Scale

Hematology				
	Grade 1	Grade 2	Grade 3	Grade 4
Hemoglobin	10.0 to 10.9 g/dL 100 to 109 g/L OR Any decrease from baseline 2.5 to < 3.5 g/dL 25 to < 35 g/L	9.0 to < 10.0 g/dL 90 to < 100 g/L OR Any decrease from baseline 3.5 to < 4.5 g/dL 35 to < 45 g/L	7.0 to < 9.0 g/dL 70 to < 90 g/L OR Any decrease from baseline ≥ 4.5 g/dL ≥ 45 g/L	< 7.0 g/dL < 70 g/L
Neutrophil (ANC)	1000 to 1300 /mm ³ 1.00 to 1.30 GI/L	750 to < 1000 /mm ³ 0.75 to < 1.00 GI/L	500 to < 750 /mm ³ 0.50 to < 0.75 GI/L	< 500 /mm ³ < 0.50 GI/L
Lymphocyte	600 to 650 /mm ³ 0.60 to 0.65 GI/L	500 to < 600 /mm ³ 0.50 to < 0.60 GI/L	350 to < 500 /mm ³ 0.35 to < 0.50 GI/L	< 350 /mm ³ < 0.35 GI/L
Platelets	100,000 to < 125,000 /mm ³ 100 to < 125 GI/L	50,000 to < 100,000 /mm ³ 50 to < 100 GI/L	25,000 to < 50,000 /mm ³ 25 to < 50 GI/L	< 25,000 /mm ³ < 25 GI/L
White Blood Cell	2000 to 2500 /mm ³ 2.00 to 2.50 GI/L	1500 to < 2000 /mm ³ 1.50 to < 2.00 GI/L	1000 to < 1500 /mm ³ 1.00 to < 1.50 GI/L	< 1000 /mm ³ < 1.00 GI/L
Blood Chemistry				
ALT (SGOT)	1.25 to 2.50 × ULN	> 2.50 to 5.00 × ULN	> 5.00 to 10.0 × ULN	> 10.0 × ULN
AST (SGPT)	1.25 to 2.50 × ULN	> 2.50 to 5.00 × ULN	> 5.00 to 10.0 × ULN	> 10.0 × ULN
Alkaline Phosphatase	1.25 to 2.50 × ULN	> 2.50 to 5.00 × ULN	> 5.00 to 10.0 × ULN	> 10.0 × ULN
Albumin	3.0 g/dL to < LLN 30 g/L to < LLN	2.0 to < 3.0 g/dL 20 to < 30 g/L	< 2.0 g/dL < 20 g/L	NA
Hyponatremia	130 to 135 mEq/L 130 to 135 mmol/L	125 to < 130 mEq/L 125 to < 130 mmol/L	121 to < 125 mEq/L 121 to < 125 mmol/L	< 121 mEq/L < 121 mmol/L
Hypernatremia	146 to 150 mEq/L 146 to 150 mmol/L	> 150 to 154 mEq/L > 150 to 154 mmol/L	> 154 to 159 mEq/L > 154 to 159 mmol/L	> 159 mEq/L > 159 mmol/L
Hypokalemia	3.0 to 3.4 mEq/L 3.0 to 3.4 mmol/L	2.5 to < 3.0 mEq/L 2.5 to < 3.0 mmol/L	2.0 to < 2.5 mEq/L 2.0 to < 2.5 mmol/L	< 2.0 mEq/L < 2.0 mmol/L
Hyperkalemia	5.6 to 6.0 mEq/L 5.6 to 6.0 mmol/L	> 6.0 to 6.5 mEq/L > 6.0 to 6.5 mmol/L	> 6.5 to 7.0 mEq/L > 6.5 to 7.0 mmol/L	> 7.0 mEq/L > 7.0 mmol/L
Hypoglycemia (Fasting)	55 to 64 mg/dL 3.03 to 3.58 mmol/L	40 to < 55 mg/dL 2.20 to < 3.03 mmol/L	30 to < 40 mg/dL 1.64 to < 2.20 mmol/L	< 30 mg/dL < 1.64 mmol/L
Calcium (Increase)	2.65 – 2.88 mmol/L	2.89 – 3.13 mmol/L	3.14 – 3.38 mmol/L	> 3.38 mmol/L

Calcium (Decrease)	1.95 – 2.10 mmol/L	1.75 – 1.94 mmol/L	1.53 – 1.74 mmol/L	< 1.53 mmol/L
Phosphorus (Decrease)	NA	2.0 to < 2.5 mg/dL 0.63 to < 0.80 mmol/L	1.0 to < 2.0 mg/dL 0.31 to < 0.630 mmol/L	< 1.0 mg/dL < 0.31mmol/L
Hyperbilirubinemia	> 1.0 to 1.5×ULN	> 1.5 to 2.5×ULN	> 2.5 to 5.0×ULN	> 5.0×ULN
Blood Urea Nitrogen	1.25 to 2.50×ULN	> 2.50 to 5.00×ULN	> 5.00 to 10.0×ULN	> 10.0×ULN
Serum Creatinine	> 1.5 to 2.0 mg/dL > 133 to 177 μmol/L	> 2.0 to 3.0 mg/dL > 177 to 265 μmol/L	> 3.0 to 6.0 mg/dL > 265 to 530 μmol/L	> 6.0 mg/dL > 530 μmol/L
Creatinine Phosphokinase	3.0 to < 6.0×ULN	6.0 to < 10.0×ULN	10.0 to < 20.0×ULN	≥ 20.0×ULN
Blood Coagulation				
Prothrombin Time	> 1.00 to 1.25×ULN	> 1.25 to 1.50×ULN	> 1.50 to 3.00×ULN	> 3.00×ULN

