### **1.3.1. Risk Assessment**

Potential Risk of Clinical Significance	Data/Rationale for Risk	Mitigation Strategy
Investigational Product (IP)		
Renal toxicity	Tenofovir is principally eliminated by the kidney. Renal impairment, including cases of acute renal failure and Fanconi syndrome (renal tubular injury with severe hypophosphatemia), has been reported with the use of VIREAD.	
 
• Exclusion of CHB patients with creatinine clearance <70 mL/min
 
• Monitor renal function every 12 weeks
 
• Dosing interval adjustment of VIREAD is recommended in all patients with creatinine clearance below 50 mL/min.
 
• Stopping criteria based on renal function with serum creatinine confirms >2.5 mg/dL have been clearly defined.(see section 6.3.2)
 

Bone events	Decreases in Bone mineral density (BMD) has been reported in adults and pediatric patients. The effects of VIREAD-associated changes in BMD and biochemical markers on long-term bone health and future fracture risk are unknown.	
 
• Monitoring the serum calcium and phosphate every 12 weeks
 
• In every regular visits, the information of bone related symptoms will be collected.
 
• Assessment of BMD and related treatment should be considered by the investigator's judgement.
 

Lactic acidosis/severe hepatomegaly with steatosis and lipodystrophy	Lactic acidosis/ severe hepatomegaly with steatosis, including fatal cases, have been reported with the use of nucleoside analogs, including VIREAD, in combination with other antiretrovirals.	
 
• Guidelines for management of lactic acidosis are outlined in Appendix 4.
 

Drug-Drug Interaction Potential	Since tenofovir is primarily eliminated by the kidneys, coadministration of VIREAD with drugs that reduce renal function or compete for active tubular secretion may increase	
 
• Estimated creatinine clearance will be assessed in all patients every 12 weeks during treatment with TDF
 
• TDF should be avoided
 

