7.5.3 Laboratory assessments

Summary tables of hematology and blood chemistry by visit will be provided including the changes from baseline for each post-baseline visits. Descriptive statistics will be used for quantitative variables. For qualitative variables, the number and percentage for each parameter will be presented.

Treatment-emergent grade 3 or grade 4 laboratory abnormalities are defined as values that increase at least one grade from baseline and get Grade 3 (severe) or 4 (potentially life threatening) at any post-baseline value (as defined in Appendix 3). If the relevant baseline laboratory data are missing, then the screening laboratory result will be used; if it is missing then any Grade 3 or 4 post-baseline values are considered treatment emergent.

The following summaries (number and percentage of subjects) of treatment-emergent laboratory abnormalities will be provided:

- Treatment-emergent Grade 3 or Grade 4 laboratory abnormalities
- Incidence of on-treatment hepatitis exacerbation defined as bilirubin ≥ 2 times ULN or albumin ≤ 3 g/dL or ALT ≥ 20 times ULN (and ≥ 2 times baseline)
- Confirmed (defined as two consecutive visits) serum creatinine ≥ 0.5 mg/dL above baseline
- Confirmed (defined as two consecutive visits) serum phosphate < 2 mg/dL
- Calculated creatinine clearance < 50 mL/min

Mean estimated glomerular filtration rate (eGFR) over time by baseline eGFR, mean creatinine

clearance rate (Ccr) over time by baseline Ccr, mean serum phosphorus over time will be analyzed by line plots, respectively.

Change of average LSM/ALT by visit, change of average LSM by visit, change of median of LSM by visit, change of average GPR/APRI/FIB-4 by visit, change of median of GPR/APRI/FIB-4 by visit, change of fibrosis stage by visit will be analyzed by line plots, respectively.

In addition, listings of hematology, blood chemistry, blood coagulation, urinalysis, pregnancy test, and alpha fetoprotein (AFP) will be provided.

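### The SAP's phosphorus grading row pairs mg/dL and mmol/L limits that do not agree and names no governing unit, so the same result can be graded in two ways

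*SAP*

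**What the plan says.** The phosphorus row of the grading scale in SAP 8.3 (Appendix 3) has no Grade 1. The other grades are printed in both units:

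- Grade 2: "2.0 to < 2.5 mg/dL 0.63 to < 0.80 mmol/L"
- Grade 3: "1.0 to < 2.0 mg/dL 0.31 to < 0.630 mmol/L"
- Grade 4: "< 1.0 mg/dL < 0.31mmol/L"

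SAP 7.5.3 uses these grades to define treatment-emergent abnormalities as "values that increase at least one grade from baseline and get Grade 3 (severe) or 4 (potentially life threatening", judged at any post-baseline value, and tabulates Grades 3 and 4 together. The same section plans a second phosphate summary in one unit only: "Confirmed (defined as two consecutive visits) serum phosphate < 2 mg/dL".

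Protocol 1.3.1 lists "Fanconi syndrome (renal tubular injury with severe hypophosphatemia" among the reported renal harms of tenofovir and gives "Monitoring the serum calcium and phosphate every 12 weeks" as a mitigation under bone events. Neither document states the unit in which the laboratory reports phosphate, or which of the two printed scales decides the grade.

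**The concern.** A grading row printed in two units should give the same grade whichever unit is used. This one does not, and the disagreement includes the boundary between Grade 2 and Grade 3. That boundary decides whether a result can enter the Grade 3 or 4 table at all. The person programming the table must pick a scale, and the SAP gives no rule for the choice.

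At stake is the count of marked hypophosphataemia, a laboratory sign of the renal tubular injury that the protocol names as a risk of the drug. The SAP's two phosphate summaries could also end up using different limits, one at 0.63 mmol/L and the other at 2 mg/dL.

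**Working it through.** **Inputs.** The paired limits come from SAP 8.3: 1.0 mg/dL with 0.31 mmol/L, 2.0 with 0.63, and 2.5 with 0.80. The molar mass of phosphorus, 30.974 g/mol, is a physical constant that the documents do not give.

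**Conversion.** mmol/L = mg/dL × 10 / 30.974 = mg/dL × 0.32285.

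| mg/dL limit | Converted, mmol/L | Printed, mmol/L | Printed value in mg/dL |
|---|---|---|---|
| 1.0 | 0.323 | 0.31 | 0.960 |
| 2.0 | 0.646 | 0.63 | 1.951 |
| 2.5 | 0.807 | 0.80 | 2.478 |

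Molar masses from 30.9 to 31.0 put 2.0 mg/dL at 0.647 to 0.645, so the choice of constant does not explain 0.63. A molar mass of 32 gives 0.3125, 0.625 and 0.781, and the phosphate ion (94.97) gives 0.105, 0.211 and 0.263. Neither reproduces the row.

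**Check without any outside constant.** If each printed mmol/L limit is a value rounded to two decimals, the factor must lie in:

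- 1.0 mg/dL: (0.31 ± 0.005)/1.0 = 0.305 to 0.315
- 2.0 mg/dL: (0.63 ± 0.005)/2.0 = 0.3125 to 0.3175
- 2.5 mg/dL: (0.80 ± 0.005)/2.5 = 0.318 to 0.322

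The second and third ranges do not overlap. Truncation does not help either: 2.0 mg/dL then needs a factor below 0.32 and 2.5 mg/dL needs at least 0.32. No single factor produces the row.

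**Which results are affected.** With two-decimal reporting in mmol/L:

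- 0.63 and 0.64 (1.951 and 1.982 mg/dL) are Grade 3 by mg/dL and Grade 2 by mmol/L.
- 0.31 and 0.32 (0.960 and 0.991 mg/dL) are Grade 4 by mg/dL and Grade 3 by mmol/L.
- 0.80 (2.478 mg/dL) is Grade 2 by mg/dL and ungraded by mmol/L.

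**Direction.** All three printed mmol/L limits are low, so no single result gets a higher grade in mmol/L than in mg/dL. The number of results at Grade 3 or 4 combined is therefore equal or lower in mmol/L. This does not carry over to every subject in the treatment-emergent table, because the baseline grade shifts as well. A baseline of 0.64 mmol/L is Grade 3 by mg/dL and Grade 2 by mmol/L. A fall to 0.55 mmol/L (1.70 mg/dL) is Grade 3 on both scales, so it is treatment-emergent only on the mmol/L limits.

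**Size, on assumptions.** The documents give no phosphate distribution. I assumed normal results with mean 0.95 to 1.15 and SD 0.14 to 0.20 mmol/L. The share of all results that move is P(below 0.6457) − P(below 0.63). For subjects I took 20 visits (240/12), half of the variance within subject, and 186 subjects, and counted those with any result below the limit, ignoring the baseline-grade rule.

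| Mean, SD (mmol/L) | Below 0.6457 | Below 0.63 | Results that move (percentage points) | Subjects ever below, 0.6457 vs 0.63 | Difference of 186 |
|---|---|---|---|---|---|
| 1.15, 0.14 | 0.016% | 0.010% | 0.006 | 0.26% vs 0.17% | 0.2 |
| 1.05, 0.17 | 0.87% | 0.67% | 0.20 | 9.3% vs 7.6% | 3.2 |
| 0.95, 0.20 | 6.41% | 5.48% | 0.93 | 39.7% vs 36.0% | 6.9 |

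These rows include the two extremes of a grid of three means (0.95, 1.05, 1.15) by three SDs (0.14, 0.17, 0.20). In the middle case, changing the between-subject share of variance from 0.3 to 0.9 moves the pair of subject percentages from 12.3% vs 9.9% to 3.2% vs 2.6%.

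**The case against.** The strongest reply is that an under-count depends on two facts the documents do not supply: that results are graded in mmol/L, and that mg/dL is the intended scale. Calcium in the same appendix is graded only in mmol/L, which hints at results in that unit. Against this, the phosphate, creatinine and albumin criteria in SAP 7.5.3 are written in mg/dL or g/dL. This stands: the size and the existence of any miscount are conditional. The mismatch itself is not.

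A reader might infer that Grade 3 hypophosphataemia is under-counted. The documents do not support that for Grade 3 alone, which loses results at its upper limit and gains some from Grade 4 at its lower limit. A reader might also infer that the error always favours the drug. That fails for the treatment-emergent table because of the baseline shift shown above. A third tempting statement is that 14% to 35% of the results below 2.0 mg/dL are misgraded. That is a share of a small tail under assumed distributions. In the 35% case only 0.016% of all results lie below 2.0 mg/dL.

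The signal also has other cover: the confirmed summary in mg/dL, a plot of mean serum phosphorus, change-from-baseline tables and full chemistry listings. This cover is partial. The confirmed summary needs two consecutive visits, while the graded table counts any post-baseline value, and the confirmed summary would inherit the error if it were programmed at 0.63 mmol/L.

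Finally, phosphorus is not the only loose row. Fasting glucose pairs 40 mg/dL with 2.20 mmol/L (2.22 by conversion) and 30 mg/dL with 1.64 (1.67). The creatinine row does convert correctly: 2.0 mg/dL is 176.8, printed as 177 µmol/L. Loose conversion is therefore not a convention of the whole table.

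**Conclusion.** The point holds as a unit mismatch in a threshold that the analysis uses. The paired limits disagree at all three boundaries, no single factor reconciles them, and the SAP names no governing unit. If grading is done in mmol/L while mg/dL is intended, which the separate 2 mg/dL summary supports but does not prove, the Grade 3 or 4 result count is equal or lower and the treatment-emergent count is probably lower. If grading is done in mg/dL, there is no miscount.

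The misgraded band at the Grade 2/3 boundary is only about 0.016 mmol/L wide. On the stated assumptions about the phosphate distribution and the variance split, the subject-level effect runs from under one to about seven of 186. No primary endpoint or hypothesis test depends on it. It is a minor correction, worth making because it concerns a safety signal that the protocol names in advance.

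**What to change.** In SAP 8.3, state one governing unit for phosphorus grading and one conversion factor, 0.3229 mmol/L per mg/dL, applied without rounding the limits. If mg/dL governs, the matching mmol/L limits are 0.323, 0.646 and 0.807. Two-decimal limits are not enough: with a limit of 0.32, a result of 0.32 mmol/L (0.991 mg/dL) would still be Grade 3 in one unit and Grade 4 in the other. In SAP 7.5.3, derive the summary of confirmed values below 2 mg/dL from the same converted value, so that the two phosphate summaries share one limit. The fasting glucose row can be checked at the same time.

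The cost is three numbers, one sentence and a small change to the grading program. If mmol/L grading would otherwise have been used and mg/dL is chosen, the reported Grade 3 or 4 phosphate count may rise slightly.

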8.4 Appendix 4: Formulas and Equations

Ccr:

Cockcroft-Gault (CG) formula:

$$Ccr = \frac{(140 - \text{Age}) \times \text{Ideal Body Weight(kg)}}{72 \times \text{Scr(mg/dL)}}$$

Note: If actual body weight (ABW) is lower than ideal body weight (IBW), ABW should be used.

Calculation Formula for IBW:

$$(\text{Male}) \text{ IBW} = 50\text{kg} + 2.3\text{kg} \times [\text{Height(Inch)} - 60]$$

$$(\text{Female}) \text{ IBW} = 45.5\text{kg} + 2.3\text{kg} \times [\text{Height(Inch)} - 60]$$

$$1 \text{ Inch} = 2.54\text{cm}$$

Scr:

$$(\text{Male}) \text{ Scr} = \text{Serum Creatinine (mg/dL)}$$

$$(\text{Female}) \text{ Scr} = \text{Serum Creatinine (mg/dL)} * 0.85$$

GFR:

Chronic kidney disease (CKD)-Epidemiology Collaboration (EPI) equation:

eGFR(mL/min per 1.73 m²) = 141 × min(Scr/κ, 1)^α × max(Scr/κ, 1)^{-1.209} × 0.993^{Age} [× 1.018 if female] [× 1.159 if black], where Scr is serum creatinine (mg/dl), κ is 0.7 for females and 0.9 for males, α is -0.329 for females and -0.411 for males, min is the minimum of Scr/κ or 1, and max is the maximum of Scr/κ or 1

Non-invasive liver fibrosis evaluation index:

GPR (gamma glutamyl transpeptidase to platelet ratio):

$$GPR = \frac{GGT(/ULN)}{PLT \text{ counts}(10^9/L)} \times 100$$

APRI (aspartate aminotransferase to platelet ratio index):

$$APRI = \frac{AST(/ULN)}{PLT \text{ counts}(10^9/L)} \times 100$$

FIB-4 (fibrosis 4 score):

$$FIB - 4 = \frac{Age(Years) \times AST(IU/L)}{PLT \text{ counts}(10^9/L) \times [ALT(IU/L)]^{1/2}}$$

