## 11.2. Appendix 2: Estimated creatinine clearance rate (CLcr) Formula and Estimated Glomerular Filtration Rate (GFR) Equation

### CLcr using Cockcroft-Gault (CG) formula:

$$\text{CLcr} = [(140 - \text{Age}) \times \text{Ideal Body Weight (kg)}] / [72 \times \text{Scr (mg/dL)}]$$

Scr = Serum Creatinine in mg/dL; for female Multiplied by the coefficient of 0.85

Note: If actual body weight (ABW) is lower than ideal weight body (IBW), ABW should be used. Calculation Formula for IBW:

$$\text{(Male) IBW} = 50\text{kg} + 2.3\text{kg} \times [\text{Height (Inch)} - 60]$$

$$\text{(Female) IBW} = 45.5\text{kg} + 2.3\text{kg} \times [\text{Height (Inch)} - 60]$$

$$1\text{ Inch} = 2.54\text{cm}$$

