5. STUDY ENDPOINTS

5.1 Primary endpoint

- The cumulative incidence of newly diagnosed hepatocellular carcinoma (HCC) at Week 240, the subject must meet one of the following criteria:
 - Without HCC before Week 24
 - A histological diagnosis of HCC (i.e. by biopsy or at post-mortem);
 - In patients with nodules > 2 cm, identification of typical HCC characteristics (hypervascular in the arterial phase with washout in the portal venous or delayed phases) by 4-phase multidetector CT scan or dynamic contrast-enhanced MRI;
 - In patients with nodules > 1 cm, identification of typical HCC characteristics by both techniques (4-phase multidetector CT and dynamic contrast-enhanced MRI).
- The cumulative incidence of disease progression at Week 240, defined as the first occurrence of any one of the following criteria:
 - An increase in Childs-Pugh score (as defined in Appendix 2) of 2 or more points from baseline;
 - An increase in Childs-Pugh score of 2 or more points, solely based on laboratory parameters (i.e. bilirubin, prothrombin time and/or albumin), confirmed between two consecutive visits at least one month apart;
 - Spontaneous bacterial peritonitis (with proven sepsis);
 - Renal insufficiency defined as a decrease in creatinine clearance to ≤ 50 mL/minute confirmed on two occasions at least one week apart (calculated from serum creatinine concentration);
 - Bleeding gastric/oesophageal varices;
 - Hepatocellular carcinoma;
 - Liver-related death.

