7.2 Subject Information

7.2.1 Demographics and baseline characteristics

Demographic include subject age, sex (Male/Female), race (Asian/Others), and baseline characteristics for subjects include subject height, weight, BMI, systolic blood pressure, diastolic blood pressure, pulse, respiratory rate, body temperature, liver stiffness measurement, LSM for patient with $ALT > ULN$ or $ALT \leq ULN$, creatinine level, serum phosphorus, eGFR, creatinine clearance rate, HBV DNA, alcohol abuse, drug abuse, history of medication hypersensitivity, family history of hepatitis B and hepatoma, liver cirrhosis, hypertension, HBeAg, Childs-Pugh score, ALT, liver biopsy, and HBV genotype. Age will be calculated as the difference of the year of informed consent date and year of birth. Percentages for categorical data will be calculated based on the number of subjects in the analysis set of the corresponding population. Descriptive statistics will be used for continuous data. Listings of demographics and baseline characteristics will also be provided.

Age (Year) = Year of Informed Consent Date - Year of Birth

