Figure	4.5.1	The Proportion (95% CI) of Subjects with HBV DNA <20 IU/mL Over Time - mITT
Figure	4.5.1.1	The Proportion (95% CI) of Subjects with HBV DNA <69 IU/mL Over Time - mITT
Figure	4.8.1.1	Mean HBV DNA Log10 IU/mL Over Time by Baseline ALT Significance - mITT
Figure	4.8.3	Distribution of HBV DNA levels Over Time - mITT
Figure	4.15.1	Kaplan-Meier Curves for Newly Diagnosed Hepatocellular Carcinoma (HCC) – mITT
Figure	4.15.1.1.1	Kaplan-Meier Curves for Newly Diagnosed Hepatocellular Carcinoma (HCC) in Subjects with Platelets <100 - mITT
Figure	4.15.1.1.2	Kaplan-Meier Curves for Newly Diagnosed Hepatocellular Carcinoma (HCC) in Subjects with Platelets >=100 - mITT
Figure	4.15.3	Kaplan-Meier Curves for Disease Progression – mITT
Figure	4.15.3.1.1	Kaplan-Meier Curves for Disease Progression in Subjects with Platelets <100 - mITT
Figure	4.15.3.1.2	Kaplan-Meier Curves for Disease Progression in Subjects with Platelets >=100 - mITT
Figure	4.18.3.1	Decline in LSM from baseline to Week 240 - mITT
Figure	5.3.1.1	Mean Estimated Glomerular Filtration Rate Over Time by Baseline eGFR - SA
Figure	5.3.1.2	Mean Creatinine Clearance Rate Over Time by Baseline Ccr - SA
Figure	5.3.2	Mean Serum Phosphorus Over Time - SA
Figure	6.1.1	Change of Average LSM/ALT By Visit - mITT
Figure	6.1.2	Change of Average LSM By Visit - mITT
Figure	6.1.3	Change of Median of LSM By Visit - mITT

GlaxoSmithKline (China) Investment Co., Ltd.
Protocol 201213

Version: 2.0
Feb 26, 2021

Figure	6.3.1	Change of Average GPR APRI FIB-4 By Visit - mITT
Figure	6.3.2	Change of Median of GPR APRI FIB-4 By Visit - mITT
Figure	6.4.1	Change of Fibrosis Stage By Visit - mITT

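### SAP 8.4 puts the female 0.85 factor on serum creatinine in the Cockcroft-Gault denominator, so every woman's calculated clearance is 1.384 times the standard value

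*SAP*

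**What the plan says.** SAP 8.4 (Appendix 4) gives clearance as (140 − age) × ideal body weight / (72 × Scr), with actual weight used where it is lower. There is no separate sex coefficient. Below the formula, Scr is measured creatinine for men and, for women, "Serum Creatinine (mg/dL)} * 0.85". The CKD-EPI entry in the same appendix defines the symbol again, without the factor: "where Scr is serum creatinine (mg/dl".

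Protocol Appendix 2 (section 11.2) has the same base formula. Its note "for female Multiplied by the coefficient of 0.85" follows the definition of Scr on the same line and does not say whether Scr or the clearance is multiplied.

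The SAP uses calculated clearance in three outputs:

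- the baseline table in section 7.2.1 ("creatinine level, serum phosphorus, eGFR, creatinine clearance rate, HBV DNA");
- the laboratory count in section 7.5.3 ("Calculated creatinine clearance < 50 mL/min");
- Figure 5.3.1.2 ("Mean Creatinine Clearance Rate Over Time by Baseline Ccr - SA").

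Separately, SAP 5.1 includes in disease progression "Renal insufficiency defined as a decrease in creatinine clearance to" 50 mL/min or less, confirmed, and cites no formula. The Protocol Summary sends the reader to Protocol Appendix 2 for that component.

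**The concern.** The female coefficient is meant to lower a woman's estimated clearance. Because Scr is in the denominator, multiplying it by 0.85 raises the estimate. The likely origin is the protocol's note, which the SAP turned into an explicit equation with the factor in the wrong place.

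The error is systematic, affects one sex and always flatters renal function. Renal toxicity is the first product risk in the protocol's risk assessment (section 1.3.1), and the clearance outputs are among those meant to show it. SAP 8.4 is also the SAP's only clearance formula, so a programmer deriving the renal progression component from laboratory data would naturally use it.

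**Working it through.** **Inputs.** The formula, the ideal-weight equations and the female Scr definition are from SAP 8.4. The 50 mL/min thresholds are from SAP 5.1 and 7.5.3, and the entry limit of 70 mL/min is from Protocol 4.3. The documents state no numerical clearance result, so there is no figure of the plan's own to reproduce.

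**1. Size of the error.** Let X = (140 − age) × weight.

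- SAP, woman: X / (72 × 0.85 × Scr)
- Standard form, woman: 0.85 × X / (72 × Scr)
- Ratio: 1 / 0.85² = 1.384, whatever her age, weight or creatinine
- Men: ratio 1.000

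**2. Effect on the thresholds.**

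| Value | Conversion | Result (mL/min) |
|---|---|---|
| Standard 50 | 50 / 0.7225 | reported as 69.2 |
| SAP 50 | 50 × 0.7225 | standard 36.1 |
| Standard 70 | 70 / 0.7225 | reported as 96.9 |
| SAP 70 | 70 × 0.7225 | standard 50.6 |

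Only women with a standard clearance above 36.1 and up to 50 are misclassified. Two assumed profiles fall there:

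- aged 60, 155 cm, 45 kg, Scr 1.0 mg/dL: SAP 58.8, standard 42.5;
- aged 50, 158 cm, 55 kg, Scr 1.2 mg/dL: SAP 62.0, standard 44.8.

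**3. Direction, checked inside SAP 8.4.** Take a woman and a man of equal age, creatinine and height. At 160 cm the ideal weights are 52.38 and 56.88 kg.

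- SAP clearance, woman/man: (52.38 / 56.88) / 0.85 = 1.083, so she gets 8% more (1.066 at 150 cm, 1.096 at 170 cm).
- With 0.85 on the clearance: 0.85 × 52.38 / 56.88 = 0.783, so she gets 22% less.
- CKD-EPI in the same appendix, Scr 1.0 mg/dL, age 50: 65.6 against 87.4 per 1.73 m², a ratio of 0.751. The ratio is below 1 at every Scr tried from 0.6 to 1.5 mg/dL (0.751 to 0.918).

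So the appendix's two renal formulas disagree on the direction of the sex difference, and moving the factor to the result removes the disagreement.

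**4. Does another output catch these women?** Section 7.5.3 also counts "Confirmed (defined as two consecutive visits) serum creatinine" at least 0.5 mg/dL above baseline, which does not use clearance. Take a woman aged 55, 160 cm, actual weight not below ideal. X/72 = 85 × 52.38 / 72 = 61.84, so her standard clearance is 0.85 × 61.84 / Scr = 52.56 / Scr and her SAP clearance is 61.84 / (0.85 × Scr) = 72.75 / Scr.

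- Standard 50 is reached at Scr 52.56 / 50 = 1.05 mg/dL; SAP 50 at 72.75 / 50 = 1.46.
- If she enters at a standard 70, her Scr is 52.56 / 70 = 0.75, and the rise count fires at 1.25, where standard clearance is 42.0.
- From 1.05 to 1.25 mg/dL neither count records her; from 1.25 to 1.46 only the rise count does.
- The fall needed from 70 is 1 − 36.125/70 = 48%, instead of 1 − 50/70 = 29%.

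This gap is widest at the entry limit. If she enters at Scr 0.55 (52.56 / 0.55, about 95 mL/min), the rise count fires at 1.05 and the gap closes.

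**The case against.** The strongest reply concerns reach. SAP 5.1 does not cite Appendix 4 for the renal component, SAP 7.4.1 dates events by diagnosis, and the Protocol Summary points to Protocol Appendix 2. There a semicolon separates the Scr definition from the 0.85 note, so the note can be read correctly. Protocol 1.3.1 has clearance assessed every 12 weeks, so sites may have determined renal events during conduct. This stands: the effect on the co-primary is conditional. It does not remove the problem, because the protocol's note is itself ambiguous and neither document says whose calculation decides.

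Second, the program is not visible and the number affected is unknown. A misclassified woman must have entered at 70 mL/min or more and then fallen into a limited range. This also stands, as a limit on the number of events at stake.

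Third, none of the clearance outputs is specified by sex, so 1.384 is not the error in a pooled mean, which depends on the unknown share of women. Proportional change from baseline within a woman is unaffected. Both are correct, but absolute levels, absolute changes, threshold counts and baseline grouping remain wrong.

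Fourth, neither document prints the formula with 0.85 on the result, and CKD-EPI is indexed to body surface while Cockcroft-Gault is not. The exact 1.384 therefore rests on the named formula and the natural reading of the protocol's coefficient. The internal comparison supports the direction only.

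**Conclusion.** The concern holds. As written, SAP 8.4 overstates every woman's creatinine clearance by 38% (factor 1.384) and in effect lowers the 50 mL/min cut-off to a standard 36.1 for women. Followed literally, it makes baseline clearance, the count below 50 mL/min and the clearance plot wrong for women.

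The renal component of disease progression is under-counted only if it is derived with this formula. The number of women missed cannot be estimated from the documents. The HCC co-primary, the sample size, and the creatinine-rise, phosphate and eGFR summaries are not affected. This is an error in a governing formula rather than missing detail, and it should be corrected before results are reported.

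**What to change.** - In SAP 8.4, delete the female Scr line and define Scr once, as measured serum creatinine, for both renal formulas. For women write Ccr = 0.85 × (140 − age) × weight / (72 × Scr).
- In Protocol Appendix 2, reword the note so that 0.85 clearly multiplies the clearance.
- In SAP 5.1, state which formula, and whether the site's or the derived calculation, decides the renal component.
- Rederive baseline clearance, the count below 50 mL/min, the clearance plot and any renal progression event taken from calculated clearance.
- Check that site-determined renal events and screening clearances used the same formula. If a site read the protocol's note as the SAP does, a woman's screening value of 70 was a standard 50.6.

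The cost is one line of SAP formula text, a sentence in SAP 5.1, one clarifying line in the protocol, one line of derivation code and the check of site calculations. The reported renal event rate in women may become less favourable, and some women may prove to have had a baseline clearance below the entry limit of 70 mL/min.
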